9.4 RECORDS TO BE KEPT AND DATA SUBMISSION SCHEDULE

9.4.1 Confidentiality of Records: The original data collection forms will be stored in secure cabinets at the originating institution. Copies of these forms will also be maintained in secure cabinets at the Data Coordinating Center.

9.4.2 Patient Consent Form: At the time of registration, three signed and dated copies of the patient Informed Consent form must be available. Non-COH institutions will FAX a copy of a signed informed consent to COH (see registration procedures in Appendix E) at the time of registration.

9.4.3 Registration Eligibility Worksheet: At the time of registration, the information requested on the On-Study/Eligibility Form will be submitted to the protocol coordinator at COH.

9.4.4 Data Collection Forms and Submission Schedule

All data will be collected using COH Biostatistics Information Tracking System (BITS) data collection forms. Copies of the completed forms will be submitted to City of Hope Department of Biostatistics, the data coordinating center, c/o the Consortium Manager for data entry and stored in a secure location. The original data collection forms will reside at the originating institution in secure location.

9.4.5 The data manager will complete the Eligibility Checklist Worksheet at the time of registration.

9.4.6 Within two weeks of registration, the data manager will complete the On-

Study Form (Form OS).

9.4.7 Within four weeks of completion of each course of treatment, the data manager must complete the following:

- Treatment and Adverse Event Form
- Supplemental Data Form (if applicable)
- Flow Sheets (These are to be submitted along with each treatment form.)

9.4.8 Each time a patient is evaluated for response and/or new follow-up information is obtained the data manager will complete the Response/Off-Study Follow-Up Form.

10. STATISTICAL CONSIDERATIONS

10.1 Study Design/Endpoints

Response rate (CR+PR) will be the primary endpoint. An underlying 20% response rate will be regarded as not sufficiently active, and the trial is designed to have little chance of missing a 40% response rate. A two-stage design will be used. In the first stage, 17 patients will be enrolled. If 4 or more respond, accrual will continue to a total of 33 patients, with 10 or more responses regarded as evidence of sufficient activity to warrant further investigation. If the true response rate is 20%, the proposed design has a 90% chance of declaring vorinostat plus rituximab insufficiently active, and a 55% chance of stopping early. If the true response rate is 40%, there is a 89% chance of concluding VORINOSTAT is sufficiently active. All patients beginning VORINOSTAT therapy will be included in response rates calculations, which will include exact binomial confidence intervals.

All reportable adverse events will be monitored by the PI and CRA, and reported as described in section 10. Reportable and non-reportable adverse events are routinely tabulated for phase II consortium trials as the reports arrive. The time to progression and overall survival will be estimated using the product-limit method of Kaplan and Meier. Toxicity information recorded will include the type, severity, time of onset, time of resolution, and the probable association with the study regimen. Tables will be constructed to summarize the observed incidence by severity and type of toxicity. Baseline information (e.g. the extent of prior therapy, extent of disease) and demographic information will be presented, as well, to describe the patients treated in this Phase II study.

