2.3.6 Use of VORINOSTAT in Lymphoma

There is good preclinical evidence to support the use of HDAC inhibitors in lymphoid malignancies. Increased histone acetylation has been shown to regulate terminal B cell differentiation, as well as to cause apoptosis via upregulation of p21^{waf-1/cip1}. Several natural agents have been shown to have HDAC inhibitory activity, however the orally bioavailable synthetic compound, suberoylanilide hydroxamic acid, has to been shown to effectively bring about increased histone acetylation in B cell malignancies. VORINOSTAT induces growth arrest and apoptosis in B cell tumor lines, at least in part via upregulation of p21^{waf-1/cip1}, in a caspase independent manner. B cell tumor lines were more sensitive to VORINOSTAT than solid tumor lines in vitro (Mitsiades, et al 2003).

In clinical trials as well, responses among patients with lymphoid malignancies were prominent. In the initial phase I study using IV VORINOSTAT, of the four responders, two were lymphoma patients (Kelly, et al, 2003) In the ongoing phase I studies, there were two responders among the seven lymphoma patients, one CR and one PR. In a Phase II trial of VORINOSTAT in cutaneous T cell lymphoma presented at this year's ASH meeting, five out of 13 patients were partial responders, and in a Phase I study presented at last year's meeting reduction in tumor size was seen in six out of 21 heavily pretreated patients with NHL and Hodgkin's lymphoma. In our ongoing phase II study of vorinostat alone in relapsed or refractory indolent lymphoma patients, at the first stage evaluation point, 4 CR, 2 PR, and several patients with prolonged stable disease were seen; the trial is currently accruing to the second stage. Thus, a combination trial with rituxan in upfront, relapsed, and refractory patients is indicated.

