2.3.7 Rituximab (IDEC-C2B8, Rituxan)

Rituximab is a chimeric IgG1 monoclonal antibody targeting the CD20 surface antigen present on both normal lymphocytes and B-cell lymphomas. The activity of this agent is multifaceted, in that it leads to direct lysis by complement activation as well as antibody dependant cell mediated cytotoxicity, triggers apoptosis, and may lead to various signaling pathway changes in targeted cells (reviewed in Cartron 2004). Aside from its direct effect, it appears to also act as a chemosensitizer by blocking IL-10 binding, leading to decreased intracellular bcl-2, and a pro-apoptotic environment (Demidem, 1997, Alas D 2001). This suggests that rituximab may synergise with vorinostat's pro-apoptotic activity. It is thus reasonable to combine the two agents, vorinostat and rituximab, in indolent lymphomas.

Given the activity seen in relapsed and refractory patients with vorinostat alone, we propose a Phase II study of vorinostat at 200 mg PO b.i.d. on a two week on, one week off schedule in patients with low grade lymphomas in combination with rituximab, at 375 mg/m² given every three weeks on day 1 of the cycle along with vorinostat. Included in this cohort are patients with low-grade lymphomas according to the Working Formulation classification, newly diagnosed or who have recurred after rituxan and/or chemotherapy.

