3. PATIENT SELECTION

3.1 Eligibility Criteria

- 3.1.1** Patients must have histologically or cytologically confirmed indolent Non-Hodgkin's Lymphoma (Included in this category are newly diagnosed or relapsed/refractory follicular center lymphomas grade I, II, III, relapsed /refractory marginal zone B-cell lymphoma (nodal and extranodal), relapsed/refractory mantle cell lymphoma).
- 3.1.2** Patients must have measurable disease by CT scan. PET scan evaluations are desirable but not mandatory, so that patients with negative PET scans but measurable disease by CT are eligible.
- 3.1.3** Patients may have had up to four prior chemotherapeutic regimens. Steroids alone and local radiation do not count as regimens (Radiotherapy must have been completed at least 14 days prior to starting vorinostat). Rituxan alone does not count as a regimen, however, Bexxar or Zevalin do. For treated patients, the most recent therapy must have failed to induce a complete response (i.e. there is persistent disease by CT or PET), or there must be disease progression or recurrence after the most recent therapy.
- 3.1.4** Patients may be enrolled who relapse after autologous stem cell transplant if they are at least three months after transplant, and after allogeneic transplant if they are at least six months posttransplant. To be eligible after either type of transplant, patients should have no active related infections (i.e. fungal or viral). In the case of allogeneic transplant relapse, there should be no active acute graft versus host disease (GvHD) of any grade, and no chronic Graft versus Host disease other than mild skin, oral, or ocular GvHD not requiring systemic immunosuppression.
- 3.1.5** Age ≥ 18 years. Because no dosing or adverse event data are currently available on the use of VORINOSTAT in patients < 18 years of age, children are excluded from this study but will be eligible for future pediatric single-agent trials, if applicable.
- 3.1.6** Life expectancy of greater than 3 months.
- 3.1.7** ECOG performance status 2 (Karnofsky $\geq 60\%$; see Appendix A).
- 3.1.8** Patients must have normal organ and marrow function as defined below:
- Absolute Neutrophil Count $\geq 1,000/\text{mcL}$
 - platelets $\geq 100,000/\text{mcL}$
 - total bilirubin within normal institutional limits; patients with elevation of unconjugated bilirubin alone, as in Gilbert's Disease, are eligible.

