10.4 Reporting and Exclusions

10.5 Evaluation of toxicity. All patients will be evaluable for toxicity from the time of their first treatment with vorinostat.

10.5.1 Evaluation of response. All patients included in the study must be assessed for response to treatment, even if there are major protocol treatment deviations or if they are ineligible. Each patient will be assigned one of the following categories: complete response, partial response, stable disease, progressive disease, early death from malignant disease, early death from toxicity, early death because of other cause, or unknown (not assessable, insufficient data).

All of the patients who met the eligibility criteria (with the possible exception of those who received no study medication) will be included in the main analysis of the response rate. Patients in any response categories other than complete response, partial response or stable disease will be considered as failing to respond to treatment (disease progression). Thus, an incorrect treatment schedule or drug administration does not result in exclusion from the analysis of the response rate.

All conclusions will be based on all eligible patients, with possible exploratory analysis of subset of patients in the event of early death due to other reasons, early discontinuation of treatment, major protocol violations, or similar circumstances requiring an assessment of the sensitivity of results. However, such subanalyses may not serve as the basis for drawing conclusions concerning treatment efficacy, and the reasons for excluding patients from the analysis will be clearly reported. Exact binomial 95% confidence intervals will be provided for response rates.

11. Correlative Studies:

Cytokine analysis

We have recently demonstrated (Li, et al PNAS, 2008) that even low doses of vorinostat dramatically decrease pro-inflammatory cytokines such as IL-2, IFN- γ , TNF- α , and IL-6. This suppression of cytokines may be of importance to the clinical effect of histone deacetylase inhibition on symptoms such as itching or the B symptoms of lymphoma, as well as potentially impacting upon lymphoma growth.

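### Does pooling newly diagnosed and relapsed/refractory patients under one response rule require a pre-specified breakdown by treatment status?

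*Combined protocol and SAP*

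**What the plan says.** Section 10.1 makes response rate (CR+PR) the primary endpoint and uses one pair of rates for the whole cohort. "An underlying 20% response rate will be regarded as not sufficiently active", and 40% is the rate the trial should rarely miss. Seventeen patients are enrolled first. With 4 or more responses accrual goes on to 33, "with 10 or more responses regarded as evidence of sufficient activity to warrant further investigation". The stated properties are a 90% chance of a negative conclusion and a 55% chance of early stopping at a true 20%, and an 89% chance of a positive conclusion at a true 40%.

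The cohort is mixed by intent. Section 3.1.1 admits "newly diagnosed or relapsed/refractory follicular center lymphomas grade I, II, III", together with relapsed/refractory marginal zone lymphoma and "relapsed/refractory mantle cell lymphoma". Section 2.3.6 argues that "a combination trial with rituxan in upfront, relapsed, and refractory patients is indicated", and section 2.3.7 describes one cohort of patients "newly diagnosed or who have recurred after rituxan and/or chemotherapy". No section fixes or caps the share of either group.

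Section 10.3 plans no stratification factors. Section 10.1 presents extent of prior therapy as baseline information. Section 10.5.1 (under the 10.4 heading) states: "All conclusions will be based on all eligible patients". It allows exploratory subsets for early death, early discontinuation, major violations and similar circumstances, and adds that "such subanalyses may not serve as the basis for drawing conclusions concerning treatment efficacy". Response, time to progression and survival by treatment status are not mentioned.

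**The concern.** A positive result is meant to justify a further study, and that study needs a population. One total can hide quite different pictures: 6/10 newly diagnosed plus 4/23 relapsed/refractory, and 3/10 plus 7/23, both make 10/33 and both meet the final rule. The first suggests going on in untreated patients only; the second suggests similar activity in both groups.

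If untreated patients respond more often, a cohort rich in them passes more easily, even when the relapsed/refractory patients respond only at the rate the plan calls inactive. Section 2.1 gives some reason to expect differences, since it says patients tend to respond initially and that disease-free intervals shorten with each line of treatment. Pooled time to progression would then depend on case mix as well. With no breakdown pre-specified, whether and how the split is shown could be settled after the results are known.

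**Working it through.** **Inputs.** From section 10.1: n1 = 17, continue if X1 ≥ 4, N = 33 (so 16 in stage 2), success if the total is ≥ 10, rates 20% and 40%. The documents give neither the case mix nor a response rate by treatment status, so those below are assumptions.

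**1. The plan's own figures.** For a true pooled rate p:

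- Early stop = P(X1 ≤ 3), X1 ~ Bin(17, p). At p = 0.20: 0.0225 + 0.0957 + 0.1914 + 0.2393 = 0.549. Stated: 55%.
- P(go) = Σ over x = 4 to 17 of P(X1 = x) · P(X2 ≥ max(0, 10 − x)), X2 ~ Bin(16, p). At p = 0.20 this is 0.099, so the chance of a negative conclusion is 0.901. Stated: 90%.
- At p = 0.40, P(go) = 0.888. Stated: 89%.

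All three are right for the pooled rate.

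**2. Dependence on case mix.** Let f be the newly diagnosed share and pN their response rate, and hold relapsed/refractory patients at 20%. Then p = f·pN + (1 − f)·0.20, entered in the same formula. Each cell gives p, then P(go).

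| pN | f = 20% | f = 30% | f = 50% |
|---|---|---|---|
| 40% | 0.24, 0.24 | 0.26, 0.33 | 0.30, 0.52 |
| 50% | 0.26, 0.33 | 0.29, 0.47 | 0.35, 0.74 |
| 60% | 0.28, 0.42 | 0.32, 0.62 | 0.40, 0.89 |

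With the mix fixed at 10 newly diagnosed and 23 relapsed/refractory (5 + 12 in stage 1, 5 + 11 in stage 2), P(go) is 0.33, 0.48 and 0.64 for pN = 40%, 50% and 60%.

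**3. What these numbers measure.** Every cell is the design's ordinary power curve read at a pooled rate between 24% and 40%. None is a false positive for the pooled question, because p exceeds 20% throughout. The last cell, 0.5 × 0.60 + 0.5 × 0.20 = 0.40, is the plan's target, where it should say go. If both groups respond at 20%, P(go) is 0.10 whatever the mix. The table also depends on holding relapsed/refractory patients at 20%: if their rate were 30%, P(go) would be 0.52 with no newly diagnosed patients at all. So the table shows a consequence of pooling. A reporting commitment would leave every entry as it is.

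**4. What a breakdown could show.** Exact (Clopper-Pearson) 95% intervals:

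| Responses | Rate | 95% CI |
|---|---|---|
| 10/33 pooled | 30% | 16% to 49% |
| 6/10 | 60% | 26% to 88% |
| 4/23 | 17% | 5% to 39% |
| 3/10 | 30% | 7% to 65% |
| 7/23 | 30% | 13% to 53% |

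Even in the split chosen for contrast, the intervals for 6/10 and 4/23 overlap between 26% and 39%. Because newly diagnosed patients are follicular only, the comparison also mixes treatment history with histology. Restricting to relapsed/refractory follicular patients lessens that but costs precision: 3/12, for instance, gives 5% to 57%. A trial stopped at 17 would leave smaller groups still.

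**The case for a change.** The best argument for a change is that it would cost almost nothing. Extent of prior therapy and histology are recorded anyway, one sentence would commit the team to showing response by treatment status, and the choice would no longer be open once results are in. Baseline tabulation reveals the mix but not who responded. The subsets foreseen in 10.5.1 do not include treatment history.

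This is true, and such a sentence would be good practice. The omission itself holds whatever response rates are assumed. But it does not make the plan unsound. Section 10.3 concerns stratification and neither requires nor rules out a table. Nothing in 10.5.1 forbids a descriptive breakdown; it bars subset results from carrying efficacy conclusions, which is the right limit for groups of this size. The objective in 1.1 is framed for subjects with indolent lymphoma as a whole. The heterogeneity argument is also weaker for the primary endpoint than for time to progression: the remark in 2.1 about shortening intervals concerns duration after further chemotherapy and gives no response rate for this regimen. Section 2.3.6, for its part, reports 4 CR and 2 PR with vorinostat alone in relapsed or refractory patients (no denominator given), so fixing that group at 20% is only one possibility.

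**Conclusion.** No change to the plan is needed. Pooling is a stated design choice, the operating characteristics are correct for the question asked, and a positive result read as 10.5.1 directs is a sound statement about the pooled cohort. The missing breakdown is a detail that analysts would ordinarily supply, since the plan already presents prior therapy and histology is confirmed at entry. Supplying it changes no threshold, sample size or error rate.

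The spread in P(go), from 0.10 to 0.89, rests on an assumed 20% rate in relapsed/refractory patients and assumed rates of 20% to 60% in newly diagnosed patients making up 20% to 50% of the cohort. It describes pooling and does not measure the effect of the missing table. If the team revises the text for other reasons, a line in 10.1 or 10.5.1 offering descriptive response rates with exact 95% intervals by treatment status would be a reasonable optional addition. Its intervals would usually be too wide to separate 20% from 40%: with 22 patients, 4 responses give 5% to 40% and 11 give 28% to 72%.

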10.2 Sample Size/Accrual Rate

Estimated monthly accrual: 3 patients

Proposed sample size: 17 to 33 patients as outlined in section 11.1

10.3 Stratification Factors

None planned.

10.4 Reporting and Exclusions

10.5 Evaluation of toxicity. All patients will be evaluable for toxicity from the time of their first treatment with vorinostat.

10.5.1 Evaluation of response. All patients included in the study must be assessed for response to treatment, even if there are major protocol treatment deviations or if they are ineligible. Each patient will be assigned one of the following categories: complete response, partial response, stable disease, progressive disease, early death from malignant disease, early death from toxicity, early death because of other cause, or unknown (not assessable, insufficient data).

All of the patients who met the eligibility criteria (with the possible exception of those who received no study medication) will be included in the main analysis of the response rate. Patients in any response categories other than complete response, partial response or stable disease will be considered as failing to respond to treatment (disease progression). Thus, an incorrect treatment schedule or drug administration does not result in exclusion from the analysis of the response rate.

All conclusions will be based on all eligible patients, with possible exploratory analysis of subset of patients in the event of early death due to other reasons, early discontinuation of treatment, major protocol violations, or similar circumstances requiring an assessment of the sensitivity of results. However, such subanalyses may not serve as the basis for drawing conclusions concerning treatment efficacy, and the reasons for excluding patients from the analysis will be clearly reported. Exact binomial 95% confidence intervals will be provided for response rates.

11. Correlative Studies:

Cytokine analysis

We have recently demonstrated (Li, et al PNAS, 2008) that even low doses of vorinostat dramatically decrease pro-inflammatory cytokines such as IL-2, IFN- γ , TNF- α , and IL-6. This suppression of cytokines may be of importance to the clinical effect of histone deacetylase inhibition on symptoms such as itching or the B symptoms of lymphoma, as well as potentially impacting upon lymphoma growth.

The effects of treatment on systemic levels of immune cytokines will be evaluated by cytokine bead array analysis using Luminex X-MAP bead array technology. This technology platform allows for the simultaneous measurement and quantification of multiple cytokines and other secreted factors from very small (10-50 μ l) samples. This analysis is sensitive (generally single pictogram level), reproducible, and accurate. The Clinical Immunobiology Correlative Studies Laboratory (CICSL) at COH is equipped with two Bioplex HTF units for these analyses.

Preassembled multiplex panels are available commercially that allow for the simultaneous evaluation of the following 30 pro- and anti-inflammatory cytokine and immune factors:

IL-1 β , IL-1RA, IL-2, IL-2R, IL-4, IL-5, IL-6, IL-7, IL-8, IL-10, IL-12p40/p70, IL-13, IL-15, IL-17, TNF- α , IFN- α , IFN- γ , GM-CSF, MIP-1 α , MIP-1 β , IP-10, MIG, Eotaxin, RANTES, MCP-1, VEGF, G-

CSF, EGF, FGF-basic, and HGF.

For these analyses, 2 ml peripheral blood will be collected prior to starting therapy, and on day 14. Whole blood will be collected in red-top tubes (Becton Dickinson) that are completely free of anti-coagulant reagents. Sample tubes should be set in an upright position at room temperature may be processed for up to 24 hours.

To process serum:

- i. Allow whole blood samples to clot for 1 – 2 hours at room temperature.
- ii. Centrifuge at 1000 x g at 4°C for 15 minutes, max brake.
- iii. Using a micropipettor, collect the serum without disturbing the red cell pellet at the bottom of the tube and transfer to a flip-top microfuge tube or a 15-mL centrifuge tube (depending on the total volume).
- iv. Freeze and store at -80°C in 100 μ L aliquots.

Luminex analysis on serum samples will be performed in bulk. Each sample will be evaluated in duplicate with the average value recorded. Quantitative values will only be determined for samples with values that fall within the 80% observed/expected range for the standard curve.

Samples should be sent to:

Clinical Immunobiology Correlative Studies Laboratory
Attn. [name]
[name]
City of Hope,
[name]

REFERENCES

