4. TREATMENT PLAN

4.1 Suberoylanilide Hydroxamic Acid (VORINOSTAT) Administration

Treatment will be administered on an outpatient basis. Reported adverse events and potential risks are described in Section 6. Appropriate dose modifications for VORINOSTAT are described in Section 5. No investigational or commercial agents or therapies other than those described below may be administered with the intent to treat the patient's malignancy.

A cycle of therapy will consist of VORINOSTAT 200mg twice daily administered orally for 14 days followed by a seven day break on a 21 day cycle for the first cycle. If tolerated, the dose may be increased after the 2nd cycle to 200 mg TID x 14/21 days. If necessary, dose de-escalation may be instituted by reducing one of the daily doses by 100 mg; so, for example, patients might receive an am dose of 300 mg and a pm dose of 200 mg. Rituximab will be infused on day 1 of each cycle at the standard dose of 375 mg/m². Radiological assessment by CT and/or PET scan will take place at baseline and after every three cycles (every 3 months). Response will be assessed by standard criteria (Cheson BD, *et al* 1999). Toxicity will be assessed on days 1 and 8 of every cycle, and graded using the NCI CTCAE version 3.0. Patients with measurable response or stable disease may continue receiving VORINOSTAT until progression. Patients who achieve CR will receive two further cycles of VORINOSTAT plus rituximab and then discontinue drug. Patients who achieve complete response may be restarted on drug in the event of relapse six months or greater from the time of initial CR, given the chronic relapsing nature of indolent lymphomas. Compliance with treatment will be monitored by use of drug diaries.

Because many drugs including antineoplastic agents are metabolized by the cytochrome P450 system, there is a potential for interaction of VORINOSTAT with concomitantly administered drugs. The case report form must capture the concurrent use of all other drugs, over-the-counter medications, or alternative therapies.

Patient compliance will be monitored using drug diaries, which will be reviewed on day 1 of each cycle after cycle 1.

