When the bone marrow was involved before therapy and a clinical CR was achieved, but with no bone marrow assessment after treatment, patients should be considered partial responders.
6. No new sites of disease should be observed.

7. Typically FDG-avid lymphoma: for patients with no pretreatment PET scan or if the PET scan was positive before therapy, the post-treatment PET should be positive in at least one previously involved site.
8. Variably FDG-avid lymphomas/FDG-avidity unknown: for patients without a pretreatment PET scan, or if a pretreatment PET scan was negative, CT criteria should be used.

In patients with follicular lymphoma or mantle-cell lymphoma, a PET scan is only indicated with one or at most two residual masses that have regressed by more than 50% on CT; those with more than two residual lesions are unlikely to be PET negative and should be considered partial responders.

Stable Disease

Stable disease (SD) is defined as the following:

1. A patient is considered to have SD when he or she fails to attain the criteria needed for a CR or PR, but does not fulfill those for progressive disease (see Relapsed Disease [after CR]/Progressive Disease [after PR, SD]).
2. Typically FDG-avid lymphomas: the PET should be positive at prior sites of disease with no new areas of involvement on the post-treatment CT or PET.
3. Variably FDG-avid lymphomas/FDG-avidity unknown: for patients without a pretreatment PET scan or if the pretreatment PET was negative, there must be no change in the size of the previous lesions on the post-treatment CT scan.

Relapsed Disease (after CR)/Progressive Disease (after PR, SD)

Lymph nodes should be considered abnormal if the long axis is more than 1.5 cm regardless of the short axis. If a lymph node has a long axis of 1.1 to 1.5 cm, it should only be considered abnormal if its short axis is more than 1.0. Lymph nodes $\leq 1.0 \times \leq 1.0$ cm will not be considered as abnormal for relapse or progressive disease.

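### Section 10.5.1 leaves stable disease out of the patients who fail to respond, contrary to the CR+PR primary endpoint in Section 10.1

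*Combined protocol and SAP*

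**What the plan says.** Section 10.1 fixes the numerator: "Response rate (CR+PR) will be the primary endpoint". It then sets a two-stage rule. Accrual continues past 17 patients if at least 4 respond, and the trial ends at 33 "with 10 or more responses regarded as evidence of sufficient activity to warrant further investigation".

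Section 10.5.1 (under 10.4, Reporting and Exclusions) gives each patient one of eight outcomes: CR, PR, SD, progressive disease, early death from lymphoma, from toxicity or from another cause, or unknown. It says which eligible patients "will be included in the main analysis of the response rate", and then classes as failures those in categories "other than complete response, partial response or stable disease will be considered as failing to respond to treatment (disease progression").

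Two other sections bear on SD. Section 8.1: "A patient is considered to have SD when he or she fails to attain the criteria needed for a CR or PR". Section 4.1 names response and SD as separate outcomes: "Patients with measurable response or stable disease may continue receiving VORINOSTAT until progression".

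**The concern.** Section 10.5.1 is the only place where the plan sorts the eight outcome categories into failures and the rest, and it puts SD on the same side as CR and PR. Under 8.1 an SD patient has not responded; under 10.5.1 the same patient is not among those failing to respond. The sentence does not call SD a response, but it does not call it a non-response either. Read as a two-way split, it contradicts 10.1.

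The decision could turn on one patient. With 9 CR+PR among 33, the regimen is insufficiently active under 10.1; adding one SD patient makes 10. With 3 CR+PR among 17, the trial stops; adding one SD patient lets it continue. The choice between readings should not be left until the data are known.

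A smaller point is the parenthetical label, which describes every failure as progression. It takes in deaths from toxicity or other causes and unknown outcomes, which the same section lists separately from progressive disease. Nothing links the label to the Kaplan-Meier analysis of time to progression, so this is a wording risk only.

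**Working it through.** **Inputs.** From Section 10.1: stage 1 has 17 patients, the total is 33 (so stage 2 has 16), continue if at least 4 respond, declare activity if at least 10 respond; null rate 20%, target rate 40%. The stated properties are 90% correct negatives and 55% early stopping at 20%, and 89% power at 40%. The SD rate is not given: Section 2.3.6 reports for vorinostat alone "4 CR, 2 PR, and several patients with prolonged stable disease were seen", with no denominator. I therefore assume SD rates of 5%, 10% and 20%.

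**Formulas.** With success probability p per patient, X1 successes in stage 1 and X2 in stage 2:

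- P(stop early) = P(X1 ≤ 3), X1 ~ Bin(17, p)
- P(active) = Σ over x from 4 to 17 of P(X1 = x) × P(X2 ≥ 10 − x), X2 ~ Bin(16, p)
- E[N] = 17 + 16 × (1 − P(stop early))

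**Step 1: reproduce the plan's figures (success = CR or PR).**

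- p = 0.20: P(stop early) = 0.5489 (stated 55%). P(active) = 0.0989, so correct negatives are 1 − 0.0989 = 0.9011 (stated 90%). E[N] = 17 + 16 × 0.4511 = 24.2.
- p = 0.40: P(active) = 0.8884 (stated 89%).

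The design is correctly calculated.

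**Step 2: count SD as success, true CR+PR still 20%.** Then p = 0.20 + SD rate, with the same formulas.

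| Assumed SD rate | p | P(stop early) | P(active) | E[N] |
|---|---|---|---|---|
| 0 (as designed) | 0.20 | 0.549 | 0.099 | 24.2 |
| 5% | 0.25 | 0.353 | 0.281 | 27.4 |
| 10% | 0.30 | 0.202 | 0.524 | 29.8 |
| 20% | 0.40 | 0.046 | 0.888 | 32.3 |

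**Step 3: how often the two readings disagree.** Counting SD can only add successes, so any trial declared active on CR+PR is also declared active with SD included. The probability of opposite conclusions is therefore the difference in P(active):

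- SD 5%: 0.2807 − 0.0989 = 0.182
- SD 10%: 0.5236 − 0.0989 = 0.425
- SD 20%: 0.8884 − 0.0989 = 0.79

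**Step 4: how little SD is needed.** Solving P(active) = target for the SD rate at a true CR+PR of 20%: the false-positive rate reaches 15% at an SD rate of 1.7%, 20% at 3.1% and 50% at 9.5%.

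**The case against.** The strongest defence is that the endpoint is not actually open. Section 10.1 names CR+PR next to the cut-offs, Section 1.1 speaks of objective response, 8.1 defines SD as falling short of response, and no section counts SD as a response. The 10.5.1 sentence can be read as a rule against dropping patients: progression, early deaths and unknowns are gathered into one failure class so that they stay in the analysis, and the sentence that follows it is about not excluding patients for treatment errors. On that reading SD keeps its own label, sits in the denominator and stays out of the numerator. The inflated error rates then describe a different endpoint, at SD rates the document does not contain. Nor does reproducing 90%, 55% and 89% settle which categories count, because those figures depend only on p and the cut-offs.

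Much of this stands. CR+PR is very probably the intent, the figures in steps 2 to 4 are conditional, and early deaths and unknowns are already failures under the present text. What does not stand is the conclusion that nothing needs correcting. The sentence sits in the rules for the main response-rate analysis, speaks of failing to respond, and draws the line in a different place from 10.1. The benign reading has to be inferred against those words, and nothing elsewhere in the document reconciles the two.

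**Conclusion.** The concern holds. Section 10.5.1 is wrong as written, because its list of non-responders omits SD and so does not match the CR+PR endpoint. The two-stage design itself is sound.

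The consequence depends on how the sentence is applied. If SD is treated as non-response, the false-positive rate stays at 9.9% and no harm follows. If SD is treated as success, at a true CR+PR of 20% the false-positive rate rises to between 28% and 89%, and early stopping falls from 55% to between 35% and 5%, over assumed SD rates of 5% to 20%. The inconsistency should be fixed before the analysis, but it is not a reason to redesign the trial.

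**What to change.** Replace the sentence in Section 10.5.1 with one to this effect: *Only complete and partial responses count as response. Stable disease, progressive disease, early death from any cause and unknown outcome count as non-response, and these patients stay in the denominator at both stages.* Delete the parenthetical reference to progression, so that unknown outcomes and deaths not due to lymphoma cannot be taken for progression events.

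The cost is a one-sentence amendment. No patients or procedures are added, and the 4/17 and 10/33 rules and their stated properties are unchanged.
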